#### **4.3 Removal of Subjects from Therapy or Assessment**

Any subject who withdraws from the study prior to completing the treatment period will be considered to have "prematurely discontinued" study participation. Subjects may withdraw or be withdrawn from the study for the following reasons:

- The subject wishes to discontinue study participation
- An adverse event or serious adverse event that imposes an unacceptable risk to the subject's health to continue in the study
- Major protocol deviations (e.g. failed to meet entry criteria, did not adhere to protocol requirements and/or impact integrity of subject level data)
- The subject is unable to tolerate 20 or 40 mg daily dose, depending on randomization
- Lost to follow up
- The subject becomes pregnant. If subjects are to withdraw due to pregnancy, the procedures in Section 7.6 should be followed
- The sponsor decides to terminate the study.

Although a subject is not obliged to give his/her reason for withdrawing prematurely, the Investigator will make a reasonable effort to obtain the reason while fully respecting the subject's rights. The procedures described for Early Termination (Section 6.1.5) will be performed, if possible. Every effort will be made to contact a subject who fails to attend a study visit, or does not respond by telephone, to ensure that the subject is in satisfactory health. The Medical Monitor will be informed of removal or early withdrawal of a subject from the study.

Withdrawn subjects will not be replaced.

If modifications in the experimental design, dosages, subject selection, etc. are indicated or required, such changes will be instituted only following consultation between the Sponsor and the Investigator and will be accomplished through formal amendments to this protocol and approval by the appropriate review committees.

This study may be discontinued at any time if, in the opinion of the Principal Investigator or the Sponsor, continuation of the study represents a significant medical risk to participating subjects.

Arbor retains the right to terminate the study at an individual study site or at all study sites for administrative reasons such as, but not limited to: unacceptable subject accrual, failure of the Principal Investigator to conduct the study according to protocol, or failure to complete study case report forms (CRFs) or maintain study records satisfactorily.

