## **9.7 Handling of Drop-Outs or Missing Data**

For subjects who discontinue prematurely, a MMRM approach will be used to address missing data. Other imputation methods (e.g., last observation carried forward [LOCF] or multiple imputation) may be used as sensitivity analyses. Full details will be described in the SAP.

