4.1.2 Full Analysis Set (FAS) Population

All subjects who are randomized, receive at least one dose of study medication, and had one or more post-Baseline on-treatment primary efficacy assessment(s) will be included in the FAS Population. The FAS Population is the primary analysis population for clinical efficacy. Results will be presented “as randomized.”

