7.1.1.2 Missing AISRS Total Scores at Individual Study Visits

Primary Analysis

No imputation of missing AISRS total scores at individual visits will be done for the primary efficacy analysis. The mixed model repeated measures methods used to analyze the primary endpoint has been designed to utilize all available data and provides valid estimates under the assumption of data which are missing completely at random or missing at random. Accordingly, all subjects with one dose of study medication and at least one post-baseline on-treatment assessment of the primary efficacy variable will be included in the model.

Sensitivity Analyses

To explore the sensitivity of the primary analysis results, analyses using two imputation methods may be performed: a placebo-based multiple imputation (MI) pattern-mixture model (PMM) analysis and a tipping point analysis using the PMM. If the dropout rate in this study is <2%, these sensitivity analyses will not be performed. This decision will be made prior to database unblinding.

Sensitivity analysis one: Placebo-based MI PMM

To explore the robustness of the primary analysis results, a sensitivity analysis will be carried out that assesses the situation where the data are not missing at random (NMAR). More specifically, all subjects taking AR19 who discontinue for any reason will be assumed to behave like placebo subjects.

A controlled, multiple imputation approach based on PMM will be applied for those subjects on AR19 using the 'Copy Reference' approach [3]. More specifically, missing data for those subjects taking AR19 who discontinued early will be imputed based on the posterior distribution of the placebo group. Missing data for placebo subjects who discontinue early will also be imputed using the observed

values of the placebo group.

Data will be imputed using SAS PROC MI (v9.3 or later) using the full conditional specification method (FCS). Twenty burn-in iterations will be performed prior to each imputation. The imputation model will include observed non-missing AISRS scores, baseline AISRS score, age, and sex. One hundred imputed datasets will be generated for analysis.

The same model used in the primary analyses will be fit to each of the 100 datasets. The parameter estimates and standard errors will be combined using PROC MIANALYZE in SAS v 9.3 or higher.

Sensitivity analysis two: Tipping Point Analysis using PMM

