The goal of the tipping point analysis is to determine how robust the results of the primary analysis are to varying its assumption that the change from baseline at Visit 7 AISRS total scores for subjects that discontinue early from the AR19 group is the same as the completers in the AR19 group. In particular, this analysis examines how altering this assumption to allow the discontinued subjects to have better and worse outcomes will impact the resulting estimates of the treatment effect. This will quantify the range of values which the assumptions can take on and still provide the same conclusions as the primary analysis, giving a very direct measure of the sensitivity of the primary analysis to deviations from the assumptions using an approach that has missing values for AR19 discontinuation subjects imputed. Missing AISRS total score data in the AR19 group will be imputed based on observed values in the AR19 group and likewise, missing AISRS total score values in the placebo group will be imputed based on observed values in the placebo group.

In this analysis, the estimate of the effect in the AR19 subjects may be viewed as a weighted average of the observed average for AR19 completers and the average MAR estimate for AR19 subjects. Shift values of .05 (treated subjects have 5% of the change from baseline AISRS total score as assumed in the primary methodology) through 1 (treated subjects have 100% of the change from baseline AISRS total score as assumed via the primary methodology) will be applied at increments of .05 and reported. The primary analysis will be rerun for all shift values and the resulting treatment difference, 97.5% CI and p-value for each shift value will be reported; the wider the range of values that result in no change in interpretation, the more robust the analysis results may be considered to be.

Subjects receiving placebo who discontinue prior to the end of the treatment period will have their change from baseline AISRS total score value imputed

based on the assumption that they respond to treatment in a similar manner to the placebo subjects who completed the study. For subjects receiving AR19 who discontinue prior to the end of the treatment period, the assumed response to treatment will be examined in increments from worst (subjects respond in a similar manner to the placebo subjects who completed the study) to best (subjects respond in a similar manner to the AR19 subjects who completed the study).

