The estimand of this primary efficacy analysis is the mean treatment difference, AR19 (20 mg/day and 40 mg/day) vs. placebo, of change from baseline in AISRS total scores among all randomized subjects who remain in the study for the duration of the blind treatment period, regardless of treatment adherence.

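### SAP 7.4.1 states the primary estimand only for subjects who stay in the study, but the planned MMRM targets a Week 5 difference that includes those who leave

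*SAP*

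**What the plan says.** SAP 7.4.1 ends by stating the estimand: the mean AR19 versus placebo difference in AISRS change "among all randomized subjects who remain in the study for the duration of the blind treatment period, regardless of treatment adherence". The Protocol states no estimand, so this is the only one in the documents.

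The rest of the primary analysis is described as follows.

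- SAP 7.4.1 runs the MMRM on the FAS, uses every observed score and imputes nothing. Protocol 9.4 says the same.
- SAP 4.1.2 admits to the FAS randomized, dosed subjects who "had one or more post-Baseline on-treatment primary efficacy assessment(s) will be included in the FAS Population". Completing the study is not required.
- SAP 7.1.1.2 says who enters the model: "all subjects with one dose of study medication and at least one post-baseline on-treatment assessment of the primary efficacy variable will be included". It also says that the method "provides valid estimates under the assumption of data which are missing completely at random or missing at random".
- Protocol 4.3 defines premature discontinuation: "Any subject who withdraws from the study prior to completing the treatment period will be considered to have" discontinued prematurely. Protocol 9.7 then says: "For subjects who discontinue prematurely, a MMRM approach will be used to address missing data".
- SAP 7.1.1.2 describes two sensitivity analyses that may be performed, and that are dropped if dropout is below 2%. In the first, "all subjects taking AR19 who discontinue for any reason will be assumed to behave like placebo subjects". The second, the tipping point analysis, gives its own account of what the primary analysis assumes: "change from baseline at Visit 7 AISRS total scores for subjects that discontinue early from the AR19 group is the same as the completers". Completers here means those of the AR19 group.
- SAP 12.2 declares no change from the analyses planned in the Protocol.

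**The concern.** Read as written, the estimand conditions on an event after randomization, namely staying to the end of the blind period. Subjects who cannot tolerate AR19 are withdrawn from the trial (Protocol 5.6, SAP 2.6), so staying can depend on the assigned treatment. A contrast among those who stay is not protected by randomization when the kind of subject who leaves, or the share who leave, differs by arm.

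The planned MMRM does not estimate that contrast. It estimates a Week 5 difference for the FAS, with later dropouts included through their observed scores and the MAR assumption. A study report that followed the estimand paragraph would therefore attach a description of one quantity to an estimate of another. At stake is the interpretation of the primary result, not its calculation.

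**Working it through.** **1. The plan's own figure.** Inputs from SAP 2.7: difference 7.0, SD 13.0, alpha 0.025 per test; the tests are two-sided (SAP 7.4.1). By the normal approximation, n = 2 × (2.2414 + 1.2816)² × 13² / 7² = 85.6, so 86 per group. By the exact t calculation, power is 0.897 at 86 and 0.900 at 87. The stated 87 reproduces. Nothing in this point alters it.

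**2. Who is in each target.**

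| Subject | Estimand paragraph | Primary MMRM |
|---|---|---|
| Completes the blind period with on-treatment scores | In | In |
| Completes, but misses or interrupts doses | In | In |
| Leaves early, at least one on-treatment AISRS after baseline | Out | In |
| Leaves early, no such AISRS | Out | Out (not in FAS) |

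The mismatch is the third row. Those are the subjects whom Protocol 4.3 calls premature discontinuations and for whom Protocol 9.7 invokes the MMRM. The fourth row shows that the FAS is also narrower than all randomized subjects, which a corrected estimand should acknowledge.

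**3. How many.** With the planned 20% dropout, 0.20 × 312 = 62.4 in total and 0.20 × 104 = 20.8 per arm fall in the third and fourth rows. The documents do not give the split between the two.

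**4. How far apart the two targets are.** In one arm, let completers have mean Week 5 change C and let dropouts, had they been measured, have mean C + D, with positive D meaning worse. If the proportion dropping out is p, the mean over all subjects in the arm is C + pD. Take benefit as placebo mean minus AR19 mean, with subscripts A for AR19 and P for placebo:

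- among those who stay: CP − CA
- among all: (CP + pP × DP) − (CA + pA × DA)
- stayers minus all: pA × DA − pP × DP

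The documents give an overall planned p of 20% but no p by arm. They give no D except through the tipping point text, which equates dropouts with completers. On that assumption D = 0 and the gap is 0. Otherwise neither size nor sign is known. Purely for scale, assume p = 0.20 in each arm and D between 2 and 10 points in one arm only. The gap then runs from 0.20 × 2 = 0.4 to 0.20 × 10 = 2.0 points, positive if that arm is AR19 and negative if it is placebo. With the same D in both arms it is 0. These D values are assumptions and set no upper bound.

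**5. What MAR actually assumes.** Under MAR, a dropout's missing Week 5 score is predicted from that subject's own observed scores within the arm. A dropout with poor early scores is predicted to do worse than the average completer. The tipping point text's description, that dropouts simply match completers, is therefore a loose account of the primary model. It does, however, show that the SAP regards dropouts as part of what the primary analysis addresses.

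**The case against.** The strongest reply is that this is labelling only. The paragraph presents itself as the estimand of the analysis just specified; a statistician following SAP 7.4.1 and 7.1.1.2 would run one analysis and obtain one p-value, and no completer analysis is planned. The drafter may have meant the difference as if everyone had remained. The documents also do not say which text governs, so calling the estimand sentence wrong is a judgement. The sensitivity analyses are conditional and cannot settle the matter.

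Most of that stands. The effect is confined to interpretation. The choice of which text to correct is an inference, though a well-supported one: the analysis sections agree with one another and with the Protocol, and SAP 12.2 disclaims any departure. The sensitivity analyses are supporting evidence only. The as-if-all-remained reading is plausible, but the sentence does not say it. The reference to adherence does not help either. It is coherent for subjects who still attend but miss or interrupt doses (SAP 6, Protocol 7.4.3) and says nothing about those who leave.

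A reader might infer two stronger things. One is that the primary analysis is a completer analysis, or is biased by conditioning on completion. It is not: no section restricts it to completers. The other is that the treatment effect is misstated by one or two points. The documents do not support that. The illustrative gaps rest on assumed values and measure the distance between two targets, one of which nobody plans to estimate.

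**Conclusion.** The mismatch is real and should be fixed before unblinding. The only statement of what the primary result means names a subset defined after randomization, and the planned FAS, MAR-based MMRM does not estimate the effect in that subset. About 62 of 312 randomized subjects, at the plan's own dropout rate, lie outside the stated target, although those with an on-treatment AISRS after baseline are analysed. The gap in points is zero if dropouts match completers and otherwise unknown.

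This does not show that MAR holds. It shows that the analysis sections are coherent with each other and the estimand sentence is not coherent with them. The MMRM, the 0.025 tests, the sample size and the p-values stay as they are.

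**What to change.** Before unblinding, replace the clause in SAP 7.4.1 that restricts the estimand to those who stay, so that the paragraph states:

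1. the target population: all randomized subjects meeting the entry criteria, with estimation in the FAS;
2. the contrast: each AR19 dose separately against placebo, in change from baseline to Week 5 in AISRS total score;
3. that missed or interrupted doses among subjects still in the study are disregarded;
4. the strategy for study discontinuation.

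The documents name no strategy for item 4. The one that matches the planned MAR model is hypothetical: the outcome as if subjects had continued in the study on their assigned treatment to Week 5. The sponsor should confirm that this is intended.

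Two conforming edits belong in SAP 7.1.1.2. The tipping point text should describe the primary assumption as MAR given observed scores, rather than as dropouts matching completers. The placebo-based analysis should be said, if performed, to use a different assumption for subjects who discontinue. The number of randomized subjects outside the FAS can be reported by arm from the disposition counts already planned in SAP 4.2.

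The cost is one rewritten paragraph and two short edits. The model, data collection and sample size do not change.

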7.4.2 Secondary Efficacy Analyses

The primary analysis will be repeated on the FAS population using the mixed model repeated measures analysis described in Section 7.4.1.

The secondary efficacy outcomes include:

- Changes from Baseline of AISRS hyperactivity/impulsivity and inattentive subscale scores compared to Visit 7
- CGI-S at Visit 7 compared to Baseline
- CGI-I at Visit 7
- Changes from Baseline of the BRIEF-A, subscales, indices, and composites compared to Visit 7

For the AISRS, the proportion of responders (defined as a subject who has a change from Baseline of 30% or greater in the AISRS) will also be presented.

The number and percentage of subjects who have each category of the CGI-S and CGI-I at each time point will be presented by treatment group. Cochran-Mantel-Haenszel row mean score tests will be used to compare the treatment groups. CGI-S and CGI-I results will also be summarized treating the responses as continuous values. A MMRM will be utilized to compare treatments at each time point. The model will include fixed effects for treatment, week, and the

treatment-by-week interaction.

BRIEF-A will be summarized descriptively over time utilizing observed and change from Baseline scores. Treatments will be compared at each time point utilizing MMRM models on change from Baseline scores. The model will include fixed effects for treatment, week, baseline value, and the treatment-by-week interaction.

7.5 Other Efficacy Analyses

Similar to the BRIEF-A, DERS and ASQ scale scores will be summarized descriptively over time utilizing observed and change from Baseline scores. Treatments will be compared at each time point utilizing MMRM models on change from Baseline scores. The model will include fixed effects for treatment, week, baseline value, and the treatment-by-week interaction.

7.6 Examination of Subgroups

The primary and secondary efficacy analyses (CGI and BRIEF-A composite scores only) will be repeated on the FAS population based on the following subgroups:

- Sex (Male, Female)
- Race (White, Black or African American, Other)
- ADHD type (Hyperactive-Impulsive, Inattentive, Combined)

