2.7 Sample Size Determination

The primary efficacy endpoint is change from Baseline in AISRS total score at Visit 7 (Week 5). A Bonferroni adjustment will be utilized for the primary efficacy analysis where each AR19 dose will be tested against placebo separately using an alpha of 0.025 for each test.

Eighty-seven (87) subjects per treatment group will provide approximately 90% power to detect a 7.0-point difference in mean change from Baseline to Visit 7 in the AISRS total score between one of the AR19 doses and placebo with a standard deviation of 13.0 and Type I error of 0.025 using a two-sample test. To account for an approximate 20% dropout rate, a total of 104 subjects will be randomized to each of the three treatment groups for a total of 312 randomized subjects.

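### SAP 7.6 repeats the efficacy analyses within subgroups and plans no treatment-by-subgroup contrast, so it cannot show whether the effect differs between strata

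*SAP*

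**What the plan says.** SAP 7.6 is the whole subgroup plan. The primary analysis and two sets of secondary analyses (CGI and BRIEF-A composite scores) "will be repeated on the FAS population based on the following subgroups", and it then lists sex (two levels), race (three) and ADHD type (three). It names no interaction term, heterogeneity test, minimum stratum size, pooling rule or exploratory label.

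Nothing elsewhere fills the gap:

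- The primary model in SAP 7.4.1 has treatment, week, baseline AISRS and treatment-by-week. Its possible adjustment for baseline imbalance is a sensitivity analysis and not a test of differing effects.
- SAP 7.4.1 applies no multiplicity adjustment beyond the two primary comparisons.
- SAP 10 plans no other analyses.
- Protocol section 9 contains no subgroup analysis.
- The default for testing is two-sided at 2.5% (SAP 3). Protocol 9.2 has 5%.

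The sample size (SAP 2.7) is set for the whole sample: "Eighty-seven (87) subjects per treatment group will provide approximately 90% power", "with a standard deviation of 13.0 and Type I error of 0.025 using a two-sample test".

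**The concern.** The natural reading of SAP 7.6 is a separate fit in each stratum, each giving its own LS-mean contrasts and p-values. A p-value within a stratum asks whether the effect is detectable there. The question that motivates a subgroup analysis is whether the effect differs between strata, and no planned output addresses it.

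Because the trial is powered for the whole sample, each stratum is underpowered. One stratum can easily reach significance while the other does not, although the true effects are the same. A reader of the study report could then conclude that the drug works in one sex, race group or ADHD type and not in another, without support from the data.

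Separate fits also re-estimate the covariance in each stratum. Under the convergence fallback in SAP 7.4.1, strata of one factor could end up analysed under different covariance structures.

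**Working it through.** **Inputs.** Difference 7.0 points, SD 13.0, alpha 0.025 per comparison, 87 per group, 104 randomised per group and 20% dropout (SAP 2.7). That leaves 104 × 0.8 = 83 per arm. Stratum sizes are not in the documents, so the splits below are assumptions. Power is from the two-sided two-sample t test (noncentral t). Strata are independent and have the same true effect.

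**The plan's own figure.** 87 per arm, difference 7, SD 13, alpha 0.025: power 90.0%. The stated figure is reproduced.

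**Two-level factor, one dose against placebo.** With stratum powers p1 and p2, the chance that exactly one stratum is significant is p1(1 − p2) + p2(1 − p1). For an even split this is 2p(1 − p).

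| Per arm | Split | Alpha | Stratum power | Exactly one significant |
|---|---|---|---|---|
| 83 (41 per sex) | 50:50 | 0.025 | 0.563 | 2 × 0.563 × 0.437 = 49% |
| 87 (43.5 per sex) | 50:50 | 0.025 | 0.592 | 2 × 0.592 × 0.408 = 48% |
| 104 (52 per sex) | 50:50 | 0.025 | 0.681 | 2 × 0.681 × 0.319 = 43% |
| 83 (66.4 and 16.6) | 80:20 | 0.025 | 0.797, 0.226 | 0.797 × 0.774 + 0.226 × 0.203 = 66% |
| 83 (41 per sex) | 50:50 | 0.05 | 0.673 | 44% |
| 104 (52 per sex) | 50:50 | 0.05 | 0.776 | 35% |

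**Larger effects.** The design effect is 7/13 = 0.54. Protocol 1.1.2 and SAP 2.1 cite mean stimulant effect sizes of 0.73 to 0.96 in adult trials. At 41 per arm per sex and alpha 0.025:

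- 0.73: power 0.844, so 2 × 0.844 × 0.156 = 26%.
- 0.96: power 0.979, so 2 × 0.979 × 0.021 = 4%.

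**Three-level factors.** With 87 per arm, a 7-point effect and alpha 0.025, the chance that the strata do not all agree is 1 − p1p2p3 − (1 − p1)(1 − p2)(1 − p3):

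- Equal thirds (power 0.406 each): 72%.
- Shares of 70/20/10 (powers 0.758, 0.238, 0.114): 82%.

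**Interaction contrast.** By construction it calls equal effects different at the nominal rate, 2.5% per dose and factor. For sex split evenly with 87 per arm:

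- SE = 13 × √(2/43.5 + 2/43.5) = 3.94.
- 97.5% interval half-width = 2.241 × 3.94 = 8.8 points.
- Power for a true 7-point difference in effect = Φ(7/3.94 − 2.241) = Φ(−0.466) = 32%.

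**Small strata.** The model has 16 fixed-effect parameters (1 intercept + 2 treatment + 4 week + 8 interaction + 1 baseline) and 5 × 6/2 = 15 covariance parameters.

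- An assumed 10% stratum has about 8 per arm, or 24 subjects. That leaves about 24 − 3 − 1 = 20 residual degrees of freedom per visit with complete data. Power there is 10%.
- With n subjects in a stratum and simple 1:1:1 assignment, the chance of an empty arm is 3(2/3)^n − 3(1/3)^n. Out of 3 × 87 = 261 subjects, a 2% stratum (5 subjects) gives 38% and a 5% stratum (13 subjects) gives 1.5%.

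**The case against.** **The rate is not a constant.** A reader might infer that equal effects will look different about half the time. The documents do not support that as a general statement. For two equal strata 2p(1 − p) cannot exceed 50%, and the design assumptions put p close to the value that maximises it. With the effect sizes the documents themselves cite, the even-split figure drops to between 26% and 4%. This objection stands, so the rate has to carry its conditions. It does not remove the point, because unequal splits and three-level factors move the figure the other way.

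**No claim is planned.** The SAP does not say that subgroup conclusions will rest on stratum p-values. The repeated analysis also gives LS-mean differences, and SAP 3 sets 97.5% intervals where intervals are shown. Strata with equal true effects would usually have overlapping intervals. This is fair: the misreading is a risk and not a stated intention. Still, what is repeated is a hypothesis test under a 2.5% default, and no output addresses the difference between strata.

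**Estimability.** A reader might infer that the smallest stratum cannot be estimated. The documents give no stratum sizes, and SAP 7.4.1 has an ordered covariance fallback. A 10% stratum would be imprecise but estimable. The problem becomes real only below roughly 3% to 5% of subjects, and an interaction model does not rescue a stratum with an empty arm either.

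**The alternative is weak.** An interaction test with 32% power can itself be misread as proof of consistency. That also stands, and it is why the estimate and its interval matter more than the p-value.

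**Conclusion.** The point holds as a gap in method: SAP 7.6 tests within strata and plans nothing that compares them. For one dose, a true 7-point effect in both sexes, SD 13, alpha 0.025 and an even split, exactly one sex is significant 43% to 49% of the time. Across the other settings examined for a two-level factor, the figure runs from 4% (standardised effect 0.96) to about 66% (80:20 split at the 7-point effect).

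These figures assume separate fits per stratum (the natural reading, though not spelled out), assumed stratum shares, and a two-sample t test standing in for the MMRM. Imprecision and differing covariance structures in small strata are possible but depend on sizes that the documents do not give. The analyses are supportive and the primary conclusion does not depend on them, so this is an improvement worth making and not a defect in the main result.

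**What to change.** Revise SAP 7.6 before unblinding:

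- For the AISRS and the other MMRM endpoints, fit one model per factor on the whole FAS. Include subgroup and treatment-by-subgroup-by-week terms, all lower-order terms, and a common covariance. For BRIEF-A, scheduled after baseline only at Visit 7 (apart from early termination), this amounts to a treatment-by-subgroup term.
- Report the Visit 7 difference with its interval in each stratum, and the treatment-by-subgroup contrast for each dose with its interval and p-value.
- Label the analyses exploratory and drop significance tests within strata, including the Cochran-Mantel-Haenszel tests for CGI.
- State that a non-significant interaction is not evidence of equal effects.

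The cost is a changed model statement and table shells, with no new data. The downsides to state are the assumed common covariance and the low power of the interaction test. The model does not cure a stratum with an empty arm, where the contrast remains non-estimable.
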